2 SCHEDULE OF ACTIVITIES

Study assessments and procedures are presented for screening in Table 2-1 and are presented for imaging assessments and procedures in Table 2-2 (Part A), Table 2-3 (Part B), and Table 2-4 (Part C).

Protocol Amendment No.: 05

Table 2-1: Screening Procedural Outline for Parts A, B, and C (IM038010)

Procedure	Screening Visit(s) (Day -30 to Day -1)	Notes
Eligibility Assessments and Related Procedures		
Informed Consent	X	A participant is considered enrolled only when a protocol-specific informed consent is signed. Must be obtained prior to performing any screening procedures.
Inclusion/Exclusion Criteria	X	
Demographics	X	
Medical History	X	Include any toxicities or allergies related to previous treatments. For Part B, all medical history relevant to MS should be obtained.
Safety Assessments		
Height, Weight, and BMI	X	BMI will be calculated.
Complete PE	X	If the Screening PE is performed within 24 hrs prior to tracer administration on Day 1, then a single complete PE is sufficient for both the Screening and Day 1 PE. See Section 9.4.1.
12-Lead ECG	X	ECGs should be recorded after the participant has been supine for at least 5 min. If the Screening ECG is performed within 24 hrs prior to tracer administration on Day 1, then a single ECG is sufficient for both the Screening and Day 1 ECG. See Section 9.4.5.
Vital Signs	X	VS (including body temperature, respiration rate, seated BP, and HR) should be measured after the participant has been resting quietly in a supine position for at least 5 min. See Section 9.4.3.
Allen's Test	X	Parts A and B only. Normal result must be documented in at least 1 arm.
C-SSRS	X	Part C only. Screening/baseline version with lifetime and 6 months review interval.
SAE Assessment	X	All SAEs must be collected from the time of signing the consent until 10 days after the last tracer administration or the final visit, whichever is later.

Table 2-1: Screening Procedural Outline for Parts A, B, and C (IM038010)

Procedure	Screening Visit(s) (Day -30 to Day -1)	Notes
		All AEs (SAEs and non-serious AEs) associated with SARS-CoV-2 infection must be collected from the date of participant's written consent. See Section 9.2.1.
Prior and Concomitant Medication Use	X	Includes prescription, over-the-counter medications, and herbal supplements. See Section 7.7.1 for Prohibited and/or Restricted Treatments.
Laboratory Tests		
HBsAg, anti-HBc, HCV Ab, HIV Serology	X	Results must be confirmed as negative prior to tracer administration on Day 1.
Hematology, Chemistry, Urinalysis, and Coagulation	X	Parts A and C participants: Participants are required to fast for at least 10 hrs prior to specimen collection. Screening results must be reviewed for eligibility prior to tracer administration on Day 1. See Section 9.4.6 for full list of clinical laboratory safety tests/assessments.
Urine Drug Screen	X	Parts A and C only. Includes amphetamines, barbiturates, benzodiazepines, cannabinoids, cocaine, methadone, and opiates.
Urine or Breath Alcohol Test	X	
Urine Cotinine Test	X	Parts A and C only.
Pregnancy Test (WOCBP only)	X	Urine or serum test. Result must be confirmed as negative prior to tracer administration on Day 1. Acceptable methods of contraception are specified in Appendix 4.
FSH Test	X	Women < 55 years for confirmation of postmenopausal status. Refer to Appendix 4.
QuantiFERON-TB Gold Plus	X	Part C only.
Imaging		
Cranial MRI Scan	X	Part B only. MRI scan should only be performed after all Screening assessments for safety, clinical laboratory tests, and medical history have established eligibility for the study. See Section 9.1.1.2.
		MRI scan with and without gadolinium contrast agent. If gadolinium contrast agent will be used during PET-MRI, gadolinium-based contrast agent is not required during Screening MRI.

Table 2-1: Screening Procedural Outline for Parts A, B, and C (IM038010)

Procedure	Screening Visit(s) (Day -30 to Day -1)	Notes
		MRI scan should be performed within 14 days of Day 1.

Abbreviations: AE, adverse event; anti-HBc, anti-hepatitis B core antibody; BMI, body mass index; BP, blood pressure; C-SSRS, Columbia-suicide severity rating scale; ECG, electrocardiogram; FSH, follicle-stimulating hormone; HBsAG, hepatitis B surface antigen; HCV Ab, hepatitis C antibody; HIV, human immunodeficiency virus; HR, heart rate; hrs, hours; MRI, magnetic resonance imaging; MS, multiple sclerosis; min, minutes; PE, physical examination; PET, positron emission tomography; SAE, serious adverse event; SARS-CoV-2, severe acute respiratory syndrome coronavirus 2; VS, vital signs; WOCBP, women of childbearing potential.

Protocol Amendment No.: 05

Table 2-2: Imaging Procedural Outline for Part A (IM038010)

Procedure	Visit 1 Day 1 ^a	Visit 2 (2 hrs to 6 days after Visit 1 tracer administration)	Safety Follow-up 3 days (± 1 day) after most recent PET Scan ^c /Early Termination ^d	Notes
Safety Assessments				
Weight Measurement	X	X		
Partial PE	X	X		PE must be done within 24 hrs of tracer administration. Symptom-based PE only.
12-Lead ECG	X	X		ECGs should be recorded after the participant has been supine for at least 5 min. ECG will be conducted prior to tracer administration and after completion of the PET scan. See Section 9.4.5.
Vital Signs	X	X		VS will be obtained before tracer administration, after PET scan completion, and prior to discharge on Visits 1 and 2. See Section 9.4.3.
Allen's Test		X		Normal result (in the arm that will be used for arterial line placement) must be documented prior to arterial line placement.
Hematology, Chemistry, Urinalysis	X	X		Participants are required to fast for at least 10 hrs prior to specimen collection. Specimens will be collected at least 1.5 hrs after the first tracer administration and at least 1.5 hours after the second tracer administration. See Section 9.4.6 for full list of clinical laboratory safety tests/assessments.
Pregnancy Test (WOCBP only)	X	X		Urine or serum test. Result must be confirmed as negative prior to tracer administration on Day 1.
Review of Emergency Contact Instructions	X	X		Prior to discharge on Visits 1 and 2.

Table 2-2: Imaging Procedural Outline for Part A (IM038010)

Procedure	Visit 1 Day 1 ^a	Visit 2 (2 hrs to 6 days after Visit 1 tracer administration) ^b	Safety Follow-up 3 days (± 1 day) after most recent PET Scan ^c /Early Termination ^d	Notes
Non-serious AE and SAE Assessments	X	X	X	All SAEs must be collected from the time of signing the consent until 10 days after the last tracer administration or the final visit, whichever is later. All AEs (SAEs and non-serious AEs) associated with SARS-CoV-2 infection must be collected from the date of participant's written consent. See Section 9.2.1.
Concomitant Medication Use	X	X	X	
Imaging Assessments and Subseq	uent Procedures			
Arterial Line Placement		X		Prior to tracer administration.
Venous Line Placement for Venous Blood Sampling (During Visit 2 PET Scan)		X		Prior to tracer administration (on the arm opposite to the tracer administration). Only in up to 2 participants (added to Part A after initiation of Part B) undergoing simultaneous arterial and venous blood sampling.
Whole-body PET-CT Scan	X			Whole-body PET-CT scan is from apex to the upper-thigh level.
Cranial PET-CT Scan or PET-MRI Scan		X		PET-CT or PET-MRI is performed, depending on equipment availability. The cranial PET scan is performed after the whole-body PET-CT scan. If scans are performed on the same day, participants are allowed to have a light meal between the whole-body PET scan and the cranial PET scan.
Check Pressure Dressing, Hand and Finger Circulation		X		After arterial line placement, throughout the PET procedure, following removal of the arterial line, and before discharge

27

Table 2-2: Imaging Procedural Outline for Part A (IM038010)

Procedure	Visit 1 Day 1 ^a	Visit 2 (2 hrs to 6 days after Visit 1 tracer administration) ^b	Safety Follow-up 3 days (± 1 day) after most recent PET Scan ^c /Early Termination ^d	Notes
Radiotracer Administration				
Overnight and Post-dose Fasting	X	X		The night before tracer administration, participants will fast for at least 8.5 hrs before tracer administration and will remain fasted until at least 1.5 hrs after tracer administration.
				If 2 tracer administrations are performed on the same day, participants can have a light meal after the first tracer administration.
¹¹ C-BMS-986196 Tracer Administration	X ^a	X ^a		Tracer is administered by a slow IV bolus prior to the whole-body PET scan and again prior to the cranial PET scan.

Abbreviations: AE, adverse event; ECG, electrocardiogram; hr, hour; IV, intravenous; min, minute; PE, physical examination; PET, positron emission tomography; PET-CT, positron emission tomography - computed tomography; PET-MRI, positron emission tomography - magnetic resonance imaging; SAE, serious adverse event; SARS-CoV-2, severe acute respiratory syndrome coronavirus 2; VS, vital signs; WOCBP, women of childbearing potential.

Protocol Amendment No.: 05

^a Prior to initiation of Part B, all Part A participants undergo Visits 1 and 2. After initiation of Part B, up to 2 participants may be added to Part A, and will not undergo Visit 1, only Visit 2. For these participants only, Visit 2 will be regarded as Day 1.

b Visit 2 tracer administration must be done at least 2 hours after and at most 6 days after Visit 1 tracer administration. If Visit 2 is performed on Days 5, 6, or 7, the site staff must contact the participant remotely (ie, by phone) on Day 4 and record AEs and concomitant medications. If 2 scans are performed on the same day, hematology and clinical chemistry sample collection, VS measurement, ECG, and review of AEs and concomitant medications are the only safety assessments that must be assessed in duplicate, and the same arterial line may be used for both scans.

^c If the interval between Visit 1 (PET Scan 1) and Visit 2 (PET Scan 2) is ≥ 4 days, 2 follow up remote contacts (ie, phone calls) must be performed. In this case, each follow up contact will be performed 3 days (± 1 day) after the most recent PET procedure.

d For participants who are prematurely discontinued from the study.

Table 2-3: Imaging Procedural Outline for Part B (IM038010)

Procedure	Visit 1 Day 1	Visit 2 (2 hrs to 6 days after Visit 1 tracer administration) ^a	Safety Follow-up 3 days (± 1 day) after most recent PET Scan ^b /Early Termination ^c		Notes
Safety Assessments					
Weight Measurement	X				
Partial PE	X	X		hrs of trace	1 and 2, PE must be done within 24 er administration. based PE only.
12-Lead ECG	X	X		has been so On days we be conducted	uld be recorded after the participant upine for at least 5 min. ith tracer administration, ECG should ted prior to tracer administration and oletion of the PET scan.
Vital Signs	X	X		administra	obtained before tracer tion, after PET scan completion, and scharge on Visits 1 and 2. n 9.4.3.
Allen's Test	X	X		arterial lin	sult (in the arm that will be used for e placement) must be documented terial line placement.
Hematology, Chemistry, and Urinalysis	X	X		at least 1.5 See Sectio	1 and 2, specimens will be collected in hours after tracer administration. n 9.4.6 for full list of clinical safety tests/assessments.

Table 2-3: Imaging Procedural Outline for Part B (IM038010)

Procedure	Visit 1 Day 1	Visit 2 (2 hrs to 6 days after Visit 1 tracer administration) ^a	Safety Follow-up 3 days (± 1 day) after most recent PET Scan ^b /Early Termination ^c	Notes	
Pregnancy Test (WOCBP only)	X	X		Urine or serum test. Result must be con as negative prior to tracer administration Day 1.	
Review of Emergency Contact Instructions	X	X		Prior to discharge on Visits 1 and 2.	
Non-serious AE and SAE Assessments	X	X	X	All SAEs must be collected from the da participant's written consent until 10 da the last tracer administration or the fina whichever is later. All AEs (SAEs and non-serious AEs) a with SARS-CoV-2 infection must be cofrom the date of participant's written coffee Section 9.2.1	ays after al visit, associated ollected
Concomitant Medication Use	X	X	X		
Imaging Assessments and Subsequ	ient Proced	ures			
Arterial Line Placement	X	X		Prior to tracer administration.	
Venous Line Placement for Venous Blood Sampling	X			Prior to tracer administration (on the arropposite to the tracer administration). Only in up to 6 participants if requested Sponsor, and only during one cranial Plypreferably during Visit 1.	l by

Table 2-3: Imaging Procedural Outline for Part B (IM038010)

Procedure	Visit 1 Day 1	Visit 2 (2 hrs to 6 days after Visit 1 tracer administration) ^a	Safety Follow-up 3 days (± 1 day) after most recent PET Scan ^b /Early Termination ^c	Notes
Cranial PET-MRI Scan or PET-CT Scan	X^d	$X^{b,d}$		PET-MRI or PET-CT is performed, depending on equipment availability. Same scan type (ie, PET-MRI or PET-CT) should be performed for both Visits 1 and 2.
Check Pressure Dressing, Hand and Finger Circulation	X	X		After arterial line placement, throughout the PET procedure, following removal of the arterial line, and before discharge.
Radiotracer Administration				
¹¹ C-BMS-986196 Tracer Administration	X	X ^e		Tracer is administered by a slow IV bolus prior to each PET scan.

Abbreviations: AE, adverse event; ECG, electrocardiogram;

hr, hour; IV, intravenous; min, minute;

PE, physical examination; PET, positron emission tomography; PET-CT, positron emission tomography computed tomography; PET-MRI, positron emission tomography magnetic resonance imaging; SAE, serious adverse event; SARS-CoV-2, severe acute respiratory syndrome coronavirus 2; VS, vital signs; WOCBP, women of childbearing potential.

Protocol Amendment No.: 05

^a Visit 2 tracer administration must be done at least 2 hours after and at most 6 days after Visit 1 tracer administration. If Visit 2 is performed on Days 5, 6, or 7, the site staff must contact the participant remotely (ie, by phone) on Day 4 and record AEs and concomitant medications. Participants who had a within 30 days prior to Day 1 must start Scan 2 on Day 1 or Day 2. If 2 scans are performed on the same day, VS measurement, ECG, and review of AEs and concomitant medications are the only safety assessments that must be assessed in duplicate, and the same arterial line may be used for both scans.

b If the interval between Visit 1 (PET Scan 1) and Visit 2 (PET Scan 2) is ≥ 4 days, 2 follow up remote contacts (ie, phone calls) must be performed. In this case, each follow up contact will be performed 3 days (± 1 day) after the most recent PET scan.

^c For participants who are prematurely discontinued from the study.

d Dynamic PET image acquisition.

^e A third administration is permissible if a PET scan has to be repeated (eg., due to failure of a prior scan).

Table 2-4: Imaging Procedural Outline for Part C (IM038010)

Procedure	Visit 1 Day 1	Visit 2 approximately 24 hrs after the last dose of BMS-986196 (Days 2-9)	Visit 3 7 Days (±2) after Visit 2/ET	Visit 4 (28 - 31 days after Visit 3)	Notes
In-person Visit to Clinical Site	X	X	X		
Phone call/Telemedicine visit				X	In-person visit is optional. Email or text messaging is not sufficient.
Safety Assessments					
Weight Measurement			X		
Partial PE	X	X	X		
12-lead ECG	X	X	X		
Vital Signs	X	X	X		
Hematology, Clinical Chemistry, Urine analysis	X		X		Participants are required to fast for at least 10 hrs prior to specimen collection. Specimens will be collected prior to tracer administration on Visits 1 and 2. See Section 9.4.6 for full list of clinical laboratory safety tests/assessments.
C-SSRS	X	X	X		Since last visit version of C-SSRS.
Review Emergency Contact Information	X	X	X		
AE and SAE assessment	X	X	X	X	All AEs and SAEs must be collected from the time of signing the informed consent form, including those thought to be associated with protocol-specified procedures and until 28 days following discontinuation of dosing.
Concomitant Medication Use	X	X	X	X	
Imaging Assessments and	d Procedu	ires			
Venous Line Placement for Blood Sampling	X	X			Prior to tracer administration (on the arm opposite to the tracer administration).

32

Table 2-4: Imaging Procedural Outline for Part C (IM038010)

	t 2-4. Imaging 1 recedurar outline for 1 art C (11/1000010)				
Procedure	Visit 1 Day 1	Visit 2 approximately 24 hrs after the last dose of BMS-986196 (Days 2-9)	Visit 3 7 Days (±2) after Visit 2/ET	Visit 4 (28 - 31 days after Visit 3)	Notes
Cranial PET/CT or PET/MRI	X	X			PET-CT or PET-MRI is performed, depending on equipment availability.
¹¹ C-BMS-986196 Tracer Administration	X	X			Tracer is administered by a slow IV bolus prior to each PET scan.
PD Assessments					
PD Sample for	X	X			At Visit 2, collected prior to radiotracer administration
Administration of Unlab	eled BMS	5-986196	1		1
Dispensing and Oral Administration of Unlabeled BMS- 986196 ^a	X				Unlabeled BMS-986196 is administered orally with food. Administration starts on Day 1 after completion of the PET procedure or on Day 2. BMS-986196 is preferably administered once; approximately 24 hrs after the (last) dose of BMS-986196, participants will undergo the second cranial PET scan. If the second PET scan cannot be performed in this time frame, it is permissible to administer a single dose of unlabeled BMS-986196 up to 7 days after the Day 1 PET (eg, in case of scheduling conflicts) or to dose unlabeled BMS-986196 QD for up to 7 days (eg, in case of synthesis failure of the PET tracer), if the Sponsor agrees. Administration must be documented and can occur on-site and/or at home according to site preference
Reconciliation of Unlabeled BMS-986196		X			See Section 7.6 for additional information on reconciliation

Protocol Amendment No.: 05

Clinical Protocol
BMS-986196
IM038010
BTKi-CNS

Table 2-4: Imaging Procedural Outline for Part O	J (1M103801	(U)
--	-------------	-----

Procedure	Visit 1 Day 1	Visit 2 approximately 24 hrs after the last dose of BMS-986196 (Days 2-9)	Visit 3 7 Days (±2) after Visit 2/ET	Visit 4 (28 - 31 days after Visit 3)	Notes
					of study intervention, drug accountability, and review of dosing diary.

Abbreviations: AE, adverse event; C-SSRS, Columbia-Suicide Severity Rating Scale; ECG, electrocardiogram; ET, end of treatment; hr, hour; PD, pharmacodynamic; PE, physical examination; PET-CT, positron emission tomography - computed tomography; PET-MRI, positron emission tomography - magnetic resonance imaging; SAE, serious adverse event; QD, once daily.

In the event that multiple procedures are required at a single time point, the following is a list of procedures from highest to lowest priority to minimize the effect of procedures on vital signs and electrocardiogram (ECG) evaluations:

Safety (12-lead ECG)
Safety (vital signs measurements)
Safety (clinical labs)

Safety assessment in response to AEs are not impacted by this priority list.

If the scheduled time for a 12-lead ECG coincides with any blood collection (ie, clinical safety labs), the blood draw should be performed as scheduled, with the 12-lead ECG being performed prior to any blood collection (up to 15 minutes earlier). ECGs will also be collected prior to the vital sign measurements.

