 Part A: After the first tracer administration (Day 1), participants will receive a second tracer administration at least 2 hours and at most 6 days and undergo cranial PET imaging using either PET-CT or PET-MRI, depending on the availability of equipment

- Part B: After the first tracer administration (Day 1), participants will receive a second tracer administration at least 2 hours and at most 6 days, and undergo cranial PET imaging using either PET-CT or PET-MRI, depending on the availability of equipment
- Part C: After the first tracer administration and cranial PET imaging (Day 1), participants will receive unlabeled BMS-986196 for oral administration on-site or at home QD for approximately 1 day (at least 1 and at most 7 days), and will undergo a second cranial PET procedure approximately 24 hours after the last dose of unlabeled BMS-986196. PET imaging will be performed with PET-CT or PET-MRI, depending on the availability of equipment

• Safety Follow-up:

- Parts A and B: Participants will be contacted remotely by phone 3 days (± 1 day) after completion of all PET scanning procedures. An in-person visit is optional.
- Part C: Participants will have 1 in-person visit 7 days after Visit 2 after completion of all PET scanning procedures and will be contacted remotely by phone 28 days (+ 3 days) after Visit 2.

Statistical Methods:

Statistical analyses in this study will be detailed in the statistical analysis plan (SAP). There are no formal statistical hypotheses for this Phase 1, open-label study. Descriptive statistics or frequency summary, as appropriate, will be used to analyze most all primary endpoints (ie, incidence, severity, seriousness, and type of adverse events; incidence of clinically significant abnormal findings; radiation dosimetry [Part A only]; test-retest repeatability [Part B only]; proportion of free brain BTK relative to baseline [Part C only]; C-SSRS [Part C only]).

Data Monitoring Committee: No

A Data Monitoring Committee will not be used in the study.

Other Committee: No

Other review committees will not be used in the study.

Brief Summary:

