986196 up to 7 days after the Day 1 PET (eg, in case of scheduling conflicts). In addition, in case of synthesis failure of PET tracer it is permissible to administered multiple doses of unlabeled BMS-986196 in order to have BMS-986196 administered 24 hours prior to the second PET scan, if Sponsor agrees. No more than 7 doses can be administered. Up to 3 dose levels of (unlabeled) BMS-986196 will be tested (15 mg, 30 mg, and 60 mg QD) and approximately 4 participants per dose level will be tested. Initially, participants will be assigned to the 30 mg dose level. After an interim review of PET results from 2 to 4 evaluable participants, the next dose level (15 mg or 60 mg) will be determined. At least 2 evaluable participants should have completed PET imaging at the second dose level before participants are assigned to the last dose level.

Safety Follow-up Period

For Part A and Part B, participants will be contacted remotely by phone (or web-call; email or text contact without verbal contact is not sufficient) 3 days (\pm 1 day) after completion of all PET scanning procedures and will be asked about AEs and concomitant medications. An in-person visit is optional. For Part C, participants will attend one in-person follow-up visit (Visit 3) 7 days after completion of all PET scanning procedures on Visit 2. During Visit 3, participants will undergo clinical assessments, have blood collected for laboratory tests, and will be asked about AEs and concomitant medications. For Visit 4, participants will be contacted remotely by phone (or web-call; email or text contact without verbal contact is not sufficient) 28 days (\pm 3 days) after completion of Visit 2 and will be asked about AEs and concomitant medications. At the discretion of the investigator, Visit 4 can be conducted in-person.

[figure not shown]
Upon completion of Visit 4 participants will have completed the study.

Safety will be assessed throughout the study by the recording of any AEs experienced during study participation.

The study design schematic is presented in Figure 5.1-1.

[figure not shown]
Figure 5.1-1: Study Design Schema

Part A - Safety, Tolerability, and Dosimetry in Healthy Participants^a

[figure not shown]

Clinical Protocol IM038010 BMS-986196 BTKi-CNS

Part B - Repeatability of ¹¹C-BMS-986196 PET in Participants with MS

Part C - Quantification of Free BTK Availability in Healthy Participants

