7.1 Study Interventions Administered

Table 7.1-1: Study Interventions

Arm Name	Part A	Part B	Part C	
Intervention Name	¹¹ C-BMS-986196	¹¹ C-BMS-986196	¹¹ C-BMS-986196	BMS-986196
Type	Small molecule PET tracer	Small molecule PET Tracer	Small molecule PET Tracer	Small molecule/OSD
Dose Formulation	Solution for IV injection	Solution for IV injection	Solution for IV injection	Tablet
Unit Dose Strength(s)	Approximately 370 MBq, equivalent to up to 20 μg	Approximately 370 MBq, equivalent to up to 20 µg	Approximately 370 MBq, equivalent to up to 20 μg	15 mg, 30 mg, and 60 mg
Dosage Level(s)	One dose level. Up to 2 doses administered with an interdose interval between 2 hours to 6 days.	One dose level. Two doses administered with an interdose interval between 2 hours to 6 days.	One dose level. Two doses administered with an interdose interval between 2 hours to 6 days.	One tablet per day.
Route of Administration	IV injection	IV injection	IV injection	Oral
Use	Experimental	Experimental	Experimental	Experimental
IMP and Non- IMP/AxMP	IMP	IMP	IMP	IMP
Sourcing	Locally synthesized by the trial site	Locally synthesized by the trial site	Locally synthesized by the trial site	Provided centrally by the Sponsor
Packaging and Labeling	Study intervention will be provided in a sterile glass vial with rubber stopper and aluminum seal. Each container will be labeled as required per country requirement.	Study intervention will be provided in a sterile glass vial with rubber stopper and aluminum seal. Each container will be labeled as required per country requirement.	Study intervention will be provided in a sterile glass vial with rubber stopper and aluminum seal. Each container will be labeled as required per country requirement.	15 mg or 30 mg or 60 mg tablets packaged in bottles of 35 tablets. Single bottles will only contain one dose strength level of tablets. Each bottle will be labeled as required per country requirements.

Protocol Amendment No.: 05

Table 7.1-1: Study Interventions

Arm Name	Part A	Part B	Part C	
Current/Former Name(s) or Alias(es)	¹¹ C-BMS-986196	¹¹ C-BMS-986196	¹¹ C-BMS-986196	BMS-986196

Abbreviations: AxMP, auxiliary medicinal product; IMP, Investigational Medicinal Product; IV, intravenous; MBq, megabecquerel; OSD, oral solid dose; PET, positron emission tomography.

The time of dose administration will be called "0" hour.

Restrictions related to food and fluid intake are described in Section 6.3.

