7.7 Concomitant Therapy

7.7.1 Prohibited and/or Restricted Treatments

Prohibited and/or restricted medications taken prior to tracer administration in the study are described below. Medications taken within 4 weeks prior to tracer administration must be recorded on the CRF.

- 1) Prior exposure to BMS-986196 within 4 weeks of ¹¹C-BMS-986196 tracer administration
- 2) Exposure to any investigational drug or placebo within 4 weeks or 5 times the elimination half life (if known), whichever is longer of ¹¹C-BMS-986196 tracer administration
- 3) Fish oil, aspirin, platelet aggregation inhibitors (including nonsteroidal anti-inflammatory drugs with such activity) and anticoagulants within 10 days prior to and within 7 days after ¹¹C-BMS-986196 tracer administration
- 4) Use of disease-modifying therapies for MS (approved, off label, or experimental), except for glatiramer acetate, interferon-β1a and interferon-β1b (Part B only)
- 5) Systemic steroid medication within 4 weeks prior to ¹¹C-BMS-986196 tracer administration.
- 6) Use of any prescription drugs within 4 weeks or 5 times the elimination half-life (if known), whichever is longer, prior to ¹¹C-BMS-986196 tracer administration. Contraceptive medication is permitted. In Part B, symptomatic therapy for MS (eg, against spasticity) is permitted.
- 7) Use of any other drugs, including over-the-counter medications and herbal preparations, within 1 week prior to ¹¹C-BMS-986196 tracer administration, except those medications cleared by the medical monitor. Paracetamol (acetaminophen) at daily doses up to 2000 mg for up to 3 days is permissible.

Administration of investigational SARS-CoV-2 vaccines is not allowed during the study. Participants may receive approved SARS-CoV-2 vaccines while continuing on study treatment at the discretion of the investigator.

Protocol Amendment No.: 05

Treatment of active SARS-CoV-2 infections or high risk exposures, including use of investigational therapies, is allowed and should be discussed with the medical monitor.

The investigator should contact and confirm agreement with the medical monitor prior to the administration of any concomitant medications that are not explicitly permitted and are not used for the emergency treatment of AEs.

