9.4.6 Clinical Safety Laboratory Assessments

• Investigators must document their review of each laboratory safety report.

A local laboratory will perform the analyses and will provide reference ranges for these tests.

Participants in Parts A and C are required to fast for at least 10 hrs prior to specimen collection.

Results of clinical laboratory tests performed on Day -1 must be available and reviewed for study eligibility, if applicable, prior to tracer administration.

Specimens will be collected at least 1.5 hrs after the first tracer administration and at least 1.5 hours after the second tracer administration.

Table 9.4.6-1: Clinical Laboratory Assessments

Hematology		
Hemoglobin		
Hematocrit		
Total leukocyte count, including differential		
Platelet count		
Chemistry		
Aspartate aminotransferase	Total protein	
Alanine aminotransferase	Albumin	
Total bilirubin	Sodium	
Direct bilirubin	Potassium	
Alkaline phosphatase	Chloride	
Amylase	Calcium	
Lipase	Phosphorus	
Lactate dehydrogenase	Magnesium	
Creatinine	Creatine kinase	
Blood urea nitrogen Creatinine clearance (Screening only)		
Uric acid		
Fasting or non-fasting glucose		
Coagulation (Screening only)		
INR		
aPTT		
Urinalysis		
Protein		
Glucose		
Blood		
Leukocyte esterase		
pH		

Protocol Amendment No.: 05

Table 9.4.6-1: Clinical Laboratory Assessments

Microscopic examination of the sediment if blood, protein or leukocyte esterase are positive on the dipstick

Serology

Serum for hepatitis C antibody, hepatitis B core antibody, hepatitis B surface antigen, HIV-1 and -2 antibody (Screening only)

Other Analyses

Test for drugs of abuse (urine; Screening and prior to Day 1 tracer administration; Parts A and C only)

Alcohol test (urine or breath; Screening and prior to Day 1 tracer administration)

Cotinine test (urine; Screening and prior to Day 1 tracer administration; Parts A and C only)

Urine or serum pregnancy test (Parts A and B only; WOCBP only; Screening and prior to Day 1 tracer administration)

FSH test (women < 55 years for confirmation of postmenopausal status; refer to Appendix 4)

QuantiFERON-TB Gold Plus (Screening; Part C only)

Abbreviations: aPTT, activated partial thromboplastin time; FSH, follicle stimulating hormone; HIV, human immunodeficiency virus; INR, international normalized ratio; WOCBP, women of childbearing potential.

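### Part C timing rules in the current protocol contradict each other on Visit 4, safety laboratory sampling and the tracer interval, and one Visit 4 wording lets the last contact precede the end of the 28-day AE period.

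*Protocol*

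**What the plan says.** All of the following is current text of Protocol Amendment 05 or the SAP.

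- **Visit 4.** The Table 2-4 column heading is "28 - 31 days after Visit 3", with Visit 3 set at 7 ± 2 days after Visit 2. Section 5.1 counts 28 days ± 3 "after completion of Visit 2 and will be asked about AEs and concomitant medications", and SAP Section 2.1 repeats this. The synopsis says participants "will be contacted remotely by phone 28 days (+ 3 days) after Visit 2", so it has no minus side. The brief summary gives 28 ± 3 days after an unnumbered last visit. Under Section 5.1, completing Visit 4 completes the study.
- **AE period.** The Table 2-4 note requires AEs and SAEs to be collected "until 28 days following discontinuation of dosing". Section 9.2.1 gives the same 28 days for SAEs in Part C.
- **Safety laboratory tests.** The Table 2-4 row is marked at Visits 1 and 3. The note in that row says "Specimens will be collected prior to tracer administration on Visits 1 and 2". Section 9.4.6, with no restriction by part, says "Specimens will be collected at least 1.5 hrs after the first tracer administration and at least 1.5 hours after the second tracer administration".
- **Tracer interval.** The Part C tracer column of Table 7.1-1 says "Two doses administered with an interdose interval between 2 hours to 6 days". Table 2-4 allows Visit 2 on Days 2-9 and a single oral dose as late as 7 days after the Day 1 scan.
- **Prior exposure.** Section 7.7.1 item 1 lists "Prior exposure to BMS-986196 within 4 weeks of" tracer administration. Part C gives that drug about 24 hours before the second tracer dose, and no exception is written.
- **Status.** The note opening SAP Section 6 says that the study was terminated early, that Part C dosing was not continued, and that the sections after it cover Parts A and B only.

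**The concern.** Part C gives healthy participants oral doses that Section 3.3 calls therapeutically relevant, so its follow-up visits and laboratory tests are working safety rules. A site cannot satisfy Table 2-4 and Section 5.1 with one Visit 4 date. A site using the early end of the Section 5.1 window makes its last scheduled contact before the protocol's own AE collection period is over.

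The laboratory conflict matters because Table 3.3.1-1 lists amylase, lipase and glucose testing as a mitigation for the pancreatic risk. The protocol does not settle whether those samples are taken at Visit 2, the visit closest to oral dosing, or whether they come before or after the tracer.

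**Working it through.** This is day counting; no sample-size formula applies.

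**Inputs.** Screening up to 30 days before tracer (synopsis). Visit 2 on Days 2-9, so 1 to 8 days after Day 1 (Table 2-4). Last oral dose about 24 hours before Visit 2, taken as 1 day. Visit 3 at Visit 2 + 5 to + 9 (Table 2-4). AE/SAE period 28 days after dosing stops. Stated Part C duration up to 10 weeks, or 70 days (synopsis).

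**1. Stated duration.** Maximum = screening + (Day 1 to Day 9) + latest Visit 4 offset from Visit 2.

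- Visit 2 anchor: 30 + 8 + 31 = 69 days; 69/7 = 9.9 weeks. This reproduces the stated 10 weeks.
- Visit 3 anchor: 30 + 8 + (9 + 31) = 78 days; 78/7 = 11.1 weeks. This does not.

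The duration statement therefore agrees with Section 5.1 and the synopsis, and disagrees with Table 2-4.

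**2. Visit 4 against the 28-day AE period.** Days from the last oral dose = offset from Visit 2 + 1. Days from the last tracer = offset from Visit 2.

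| Source | Visit 4, days after Visit 2 | Earliest, after last oral dose | Earliest, after last tracer | Shortfall against 28 days |
|---|---|---|---|---|
| Section 5.1, SAP 2.1 | 28 − 3 = 25 to 28 + 3 = 31 | 26 | 25 | 2 (oral) or 3 (tracer) |
| Synopsis | 28 to 31 | 29 | 28 | none |
| Table 2-4 | 5 + 28 = 33 to 9 + 31 = 40 | 34 | 33 | none |

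The first and third windows (25-31 and 33-40) do not overlap. The 28-day rule does not say whether dosing means the oral drug or the tracer; the ± 3 wording falls short on either reading.

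**3. Laboratory tests.** The grid gives Visits 1 and 3. Its note gives Visits 1 and 2, before tracer. Section 9.4.6 gives at least 1.5 hours after each tracer dose, which in Part C means Visits 1 and 2. The note and Section 9.4.6 agree on the visits but not on the order relative to tracer. The grid differs from both on the second visit. On the grid alone, the first post-dose sample is at Visit 3, which is 5 + 1 = 6 to 9 + 1 = 10 days after the last oral dose.

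**4. Tracer interval.** Interval = Visit 2 day − 1. Days 2 to 7 give 1 to 6 days, within Table 7.1-1. Day 8 gives 7 and Day 9 gives 8, both above 6. The dosing rule leads to the same maximum: an oral dose 7 days after the Day 1 scan plus about 1 day is 8 days.

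**The case against.** The strongest reply is that the protocol says which text sets timing. Section 9.4 refers to the Schedule of Activities for all safety time points, Section 9 makes adherence to it essential, and Section 5.3 defines completion by its last assessment. On that footing Table 2-4 controls Visit 4, the AE shortfall disappears, and Days 2-9 override the 6-day interval. This narrows the ambiguity but does not remove it. Section 5.1, the SAP and the stated duration all follow the Visit 2 anchor, and the laboratory conflict lies partly inside Table 2-4, where the Schedule cannot settle it.

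Four further limits stand.

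- The 28-day duty is stated independently of Visit 4, and related SAEs stay reportable afterwards (Section 9.2.1). An early call puts at risk events in the last 2 to 3 days that nobody asks about; it does not end the duty to collect them.
- The blank Visit 2 laboratory cell could be an artefact of reading the table from PDF. The conflict between the note and Section 9.4.6 does not depend on it.
- A reader might infer that every Part C participant breaches Section 7.7.1 by design. Item 1 concerns prior exposure and reads naturally as a pre-study washout. Reading it literally would also make item 2, on any investigational drug within 4 weeks, forbid the second tracer dose in Parts A and B. The missing exception is a minor drafting gap.
- A reader might infer that these conflicts could remove compliant Part C participants from the Per-Protocol 3 set. Protocol Section 10.3 does include Part C in it, but SAP Table 6.3-1 limits it to Part B, it excludes only for major important deviations, and SAP Section 7.5 uses it only for optional sensitivity analyses. That consequence is not supported.

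**Conclusion.** The concern holds as an internal contradiction in the current Part C text. The Visit 4 windows of Table 2-4 and Section 5.1 are mutually exclusive. The laboratory timing is stated in three incompatible ways. The 6-day tracer interval conflicts with Visit 2 on Days 8-9 only.

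It would be wrong to infer that AE follow-up is cut short under every wording. The shortfall is 2 to 3 days and arises only from the ± 3 days counted from Visit 2; Table 2-4 and the synopsis both cover 28 days. The figures assume that about 24 hours is 1 day and count elapsed days. Counting both end days adds one to each duration (70 and 79 days), and only the Visit 2 anchor still fits 10 weeks.

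Practical impact depends on whether anyone entered Part C. The SAP says that dosing was not continued, without saying that no one was dosed. If no one was, what remains is a correction for the record.

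**What to change.** Reconcile Table 2-4, the synopsis (with its brief summary), Section 5.1, Table 7.1-1, Section 7.7.1, Section 9.4.6 and the study description in SAP Section 2.1, so that Part C has:

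- one Visit 4 anchor and window, consistent with the protocol's own 28-day AE period, meaning that it does not open before that period has elapsed;
- one set of laboratory visits, with one stated time relative to tracer;
- one tracer interval, consistent between Table 7.1-1 and the Visit 2 day range;
- a clear statement of whether Section 7.7.1 item 1 applies to protocol dosing;
- a stated study duration that matches the chosen Visit 4 timing.

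The sponsor decides which version applies in each case. Separately, state in the SAP or study report whether anyone entered Part C and, if so, which Visit 4 and laboratory schedule was applied to them.

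The cost is a text correction with no added participants. If the laboratory text is reconciled to the note or to Section 9.4.6, a Visit 2 sample is needed that the grid does not mark.
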